2.2 Aims

K99 phase

Primary Aim 1a: Characterize barriers and facilitators of glycemic control in Chinese Americans with T2D

Primary Aim 1b: Develop culturally and linguistically tailored SMS intervention content

Primary Aim 1c: Assess the feasibility and acceptability of the SMS intervention

R00 phase

Primary Aim 2a: Establish the proof-of-concept regarding the efficacy of the SMS intervention for glycemic control in Chinese Americans with T2D

Exploratory Aim 2b: Explore the potential effects of the SMS intervention on psychosocial and behavioral factors in glycemic control.

Rutgers Mental Health Pilot

Exploratory Aim 2c: Examine current mental health burden and psychosocial support and how they are related to diabetes self-care behaviors and glycemic control in Chinese Americans with T2D (via validated surveys)

Exploratory Aim 2d: Characterize barriers to accessing mental health services and understand needs and preferences in Chinese Americans with T2D (via focus groups)

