4.3.3 R00 Phase Pilot RCT Procedures

The R00 phase study is a pilot randomized controlled trial (RCT) of 6 months duration. Participants will be randomized to one of 2 arms (n=30 each): 1) wait-list control; or 2) SMS intervention. The study will include 3 measurement visits, baseline, 3, and 6 months. Patients will be paid \$30 for each measurement visit.

Upon receiving the referral list (interested patient's name and phone number) from the providers, the bilingual study staff will call the patient and provide more details about the study. If patients expressed interest in participation, the study staff will administer several screening questions over the phone. After eligibility is determined and verbal consent is obtained, we will collect baseline surveys over the phone and randomize them via a computer-generated randomization scheme with equal allocation to one of the 2 groups: 1) wait-list control; or 2) SMS.

Independent variable: randomization arm

Wait-list control group: All participants will continue to receive the standard of usual care for their T2D at their providers' office during the course of our study. At the end of the study, the wait-list control group will be provided the opportunity to receive the counseling videos delivered to them via SMS links.

SMS intervention: Participants in the intervention group will receive SMS-based video counseling, which include both educational and SCT-based behavioral content (see Table 1 below for a tentative outline of the intervention content). Given the system and personal barriers, we believe this SMS-based approach will improve access to culturally and linguistically tailored diabetes counseling. Additionally, this approach will allow participants to review the videos later on or share with their loved ones who often want to be supportive but do not know how. We will send 2 videos each week for a total of 12 weeks with each video about 5-10 minutes in duration. The videos will be sent via WeChat or regular text messages (SMS). We will contact participants mainly through phone calls from an NYU Langone Study Phone. WeChat will be only used to send the health education videos. No other communication will occur via WeChat. Our study team will remind participants at the beginning of the study and

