| 12 | Review of lifestyle recommendations | Problem solving: Anticipating high-risk situations |

Procedures: The study will include 3 measurement phone calls, baseline, 3, and 6 months. Patients will be paid \$30 for each measurement call. Due to COVID-19, all data will be collected over the telephone. Each survey calls will include audio/Video recordings if verbal consent from the study participants was obtained. For participants randomized to the SMS intervention group, we will reimburse \$5 each week to each participant for cell phone data usage if they finish viewing both of the sent videos for that week. Given that we will send videos over a total of 12 weeks, participants may expect to receive a range of \$0-\$60 ($=\$5*12$) depending on the number of weeks they have completed the videos. We will also provide \$60 to control participants if they finish all study related procedures at 3 months assessment.

Study Variables

covariates

[figure not shown]

Figure 1. Conceptual Model

Primary & Exploratory Outcomes

Primary outcome: HbA1c: As part of the usual care, patients with T2D receive a HbA1c blood test at their doctors' office every 3-6 months. To minimize participants' burden, we will not conduct additional blood tests for this study. Instead, we will abstract the HbA1c testing results from the medical record at the participant's health care facility. Once we obtain the consent from participants, we will contact their doctors' offices for HbA1c results.

Secondary outcomes: Consistent with our conceptual model (Fig. 1), we will also measure self-efficacy, diabetes self-management behaviors, dietary intake, and physical activities at each time points (baseline, 3-, and 6-months). All of these scales have been used and validated in the Chinese population.

1. **Self-efficacy:** We will use the well-validated Stanford Diabetes Self-Efficacy Scale⁴² to measure participants' confidence to manage T2D. This instrument contains 8 items and asks participants to rate their confidence level in performing specific self-management behaviors, using 10-point Likert scale ranging from 1 (not at all confident) to 10 (totally confident).

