7. DATA ANALYSIS AND DATA MONITORING

7.1 Data Analysis

K99-phase Aim 1: All focus groups will be audio-recorded and transcribed verbatim into Microsoft Word. Atlas will be used to store, organize, retrieve, and analyze the qualitative data. Thematic analysis will be used to analyze qualitative data.⁶¹ To establish coding reliability, the RA and PI will independently code up to 10% of the transcripts and identify kappa coefficient.⁶² We will meet weekly to review definitions and assignment of codes, and resolve differences through consensus. If no agreement can be made, the study team will be consulted. The RA and PI will read all transcripts and develop an open coding schema based on emergent theses. We will present coding schemes to study team, discuss emergent themes, refine codes, and develop a codebook that consists of a list of categories and topics. Once all data have been coded based on the codebook, codes most relevant to the research questions will be subject to further analysis. For the quantitative data, a paired t-test will be used to determine pre-post change in HbA1c. Descriptive statistics will be used to summarize participants' satisfaction with the SMS intervention.

R00-phase Aim 2: We will employ the "intent to treat" (ITT) approach in analyses. We will perform a detailed descriptive analysis of all the data collected in the study. These preliminary descriptive statistics will be used to 1) check accuracy and completeness of inputted data, 2) describe univariate distribution of each variable at baseline, and 3) examine the associations between variables. We will also explore features of the data (e.g., amount and pattern of missing data, outliers, excess zeros, departures from distributional assumptions) to determine whether special techniques are needed.

Aim 2a: Establish the proof of concept regarding the efficacy of the SMS intervention for glycemic control in Chinese Americans with T2D. We will test whether the 2 groups are comparable on baseline sociodemographic, health characteristics, and levels of acculturation. If significant differences are found, we will include the variables as covariates in the models. Between group and group by time interaction effects will be examined graphically and via linear mixed modeling for HbA1c. Calculated effect sizes will be used for sample size estimation needed for a two-sided alpha of 0.05 and power of 0.80 for the larger scale R01 study.

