Exploratory Aim 2b: Explore the potential effects of the SMS intervention on psychosocial and behavioral factors in glycemic control. For continuous secondary outcome variables (self-efficacy, adherence, and dietary data), linear mixed modeling will be used to examine the group and group by time interaction effects for each outcome at 3- and 6-months. For the physical activity data, we will use a GEE logistic model to examine whether there are group differences in the proportions of participants achieving 150 minutes/week of physical activity at any level of intensity and at a moderate- or greater intensity level.

Rutgers Mental Health Pilot

Aim 2c: Examine current mental health burden and psychosocial support and how they are related to diabetes self-care behaviors and glycemic control in Chinese Americans with

T2D. We will use descriptive statistics to summarize mental health burden and psychosocial support in Chinese immigrants with T2D. We will describe the percent of the sample who has elevated stress, anxiety and depressive symptoms and the current social support and coping strategies. We will also use correlation to examine the relationships between the mental health burden and diabetes self-management behaviors and HbA1c (measured in R00 study).

Aim 2d: Characterize barriers to accessing mental health services and understand needs and preferences in Chinese Americans with T2D. Similar to the analytic approach used in the K99 Aim 1 analyses, all focus groups will be audio-recorded and transcribed verbatim into Microsoft Word. Atlas will be used to store, organize, retrieve, and analyze the qualitative data. Thematic analysis will be used to analyze qualitative data.⁵⁹

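### The physical-activity GEE does not adjust for baseline activity and names no post-randomisation contrast, so its estimand is open and available precision is lost

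*Combined protocol and SAP*

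**What the plan says.** Section 2.2 states Exploratory Aim 2b as "Explore the potential effects of the SMS intervention on psychosocial and behavioral factors in glycemic control". Section 4.3.3 measures the secondary outcomes, including "dietary intake, and physical activities at each time points (baseline, 3-, and 6-months", and places the baseline survey ahead of allocation: "we will collect baseline surveys over the phone and randomize them via a computer-generated randomization scheme with equal allocation".

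Section 7.1 then treats the Aim 2b outcomes in two adjacent sentences. For the continuous ones, "linear mixed modeling will be used to examine the group and group by time interaction effects for each outcome at 3- and 6-months". For physical activity, "we will use a GEE logistic model to examine whether there are group differences in the proportions of participants achieving 150 minutes/week", at any intensity and at moderate or greater intensity.

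The activity sentence gives no time term, interaction, set of visits, baseline term or working correlation. The only covariate rule in section 7.1 sits under Aim 2a. It covers sociodemographic, health and acculturation variables, applies only when a baseline difference is significant, and does not name the baseline value of the outcome.

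**The concern.** An effect of the videos can appear only after randomisation. A GEE is a repeated-measures model and three visits are collected, so an analyst could reasonably enter all three as responses and test the one effect that is named, group. That test compares the arms on an average that includes a visit before any intervention. Another analyst could model the follow-up visits alone. The two would estimate different quantities from the same sentence, and neither would use the participant's own baseline status, which is usually the strongest available predictor of later status.

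At stake are precision and a clear estimand. With 30 per arm, sizeable chance differences in the baseline proportion are common enough to matter when the result is read.

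**Working it through.** **Inputs from the documents.** 30 per arm ("Participants will be randomized to one of 2 arms (n=30 each"); visits at baseline, 3 and 6 months; baseline before randomisation. The documents give no proportion, effect, correlation or power for this outcome, so there is no figure of the plan's own to reproduce. Two-sided 0.05 is assumed; section 7.1 states it only for sizing the later trial.

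**Assumed inputs.** Control and baseline proportion 0.2 to 0.5; gain *d* of 10 to 40 points in the SMS arm at both follow-ups; exchangeable correlation ρ of 0.3 to 0.7; complete data.

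**Dilution.** The expected baseline difference is zero, so the three-visit average effect is (0 + *d* + *d*)/3 = 2*d*/3.

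**Worked case: 40% to 60%, ρ = 0.5.** The variance is σ² = 0.24 at every visit, since 0.4 × 0.6 = 0.6 × 0.4. Power is Φ(effect/SE − 1.96), with SE = √(2V/30) and V the per-person variance of the contrast.

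- Three-visit average: V = σ²(1+2ρ)/3 = 0.16; SE = 0.1033; effect = 0.1333; z = 1.29; power 25%.
- 3/6-month average, unadjusted: V = σ²(1+ρ)/2 = 0.18; SE = 0.1095; effect = 0.20; z = 1.83; power 45%.
- 3/6-month average, baseline-adjusted: V = σ²[(1+ρ)/2 − ρ²] = 0.12; SE = 0.0894; z = 2.24; power 61%.
- Group-by-(follow-up versus baseline), 1 df: V = σ²[(1+ρ)/2 + 1 − 2ρ] = 0.18; power 45%.

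Here the three-visit test loses 61 − 25 = 36 points against the adjusted analysis. The follow-up-only test loses 61 − 45 = 16.

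**Range by the same approximation.** For gains of 20 to 30 points and ρ of 0.3 to 0.5, the three-visit loss against the adjusted analysis is 25 to 45 points, and the follow-up-only loss is about 5 to 17. Over the whole grid the three-visit loss is 7 to 60.

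**Check by simulated logistic GEE** (30 per arm, exchangeable, robust SE, 300 runs per row, Monte Carlo SE up to about 3 points). Power in %:

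| Setting (ρ between binary responses) | Three-visit group | 3/6-month unadjusted | 3/6-month adjusted | Interaction, 1 df | Interaction, 2 df |
|---|---|---|---|---|---|
| 40→60 (0.33) | 28 | 44 | 51 | 32 | 22 |
| 40→60 (0.49) | 30 | 47 | 58 | 42 | 32 |
| 40→70 (0.32) | 62 | 84 | 88 | 63 | 52 |
| 40→70 (0.49) | 54 | 78 | 90 | 73 | 57 |
| 30→40 (0.33) | 13 | 17 | 20 | 11 | 12 |

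A further run at 40% to 65% (400 runs, latent correlation 0.4/0.6/0.8) gave 0.68/0.68/0.61 for follow-up only and 0.73/0.78/0.80 adjusted, a shortfall of 5, 10 and 19 points. The shortfall falls to 3 or 4 points where power is already near its ceiling or very low, as in the third and fifth rows of the table.

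**No effect (40% in both arms, 400 runs, latent correlation 0.4/0.6/0.8).** Overall rejection was 0.050/0.050/0.062 for the three-visit test and 0.080/0.052/0.065 for the adjusted test. Among trials with a baseline gap of at least 20 points (about 15% of trials, 56 to 67 per setting), the three-visit test rejected 0.19/0.29/0.30 of the time and the adjusted test 0.04/0.04/0.08.

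**The case against.** The strongest reply is that nothing places baseline in the GEE response. Section 4.3.3 says when activity is measured, not how it is modelled, and the sentence just before the GEE sentence speaks of effects at 3 and 6 months. This stands. A reader might infer that the planned test is known to average in pre-randomisation status; the documents leave that open, and the defect is an unspecified model.

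A reader might also infer that the plan deliberately drops the interaction for activity and that this omission causes the power loss. Neither is supported. The Abstract (section 1) lists physical activity among the secondary outcomes and then refers to group and group-by-time effects, though through a linear mixed model, so it does not settle the GEE. In the simulated settings behind the table, adding the interaction alone changed power by −3 to +19 points (1 df) or −10 to +8 (2 df). It recovered about 32 points only at a latent correlation of 0.8 in the 40% to 65% setting. The gain comes mainly from a follow-up contrast with baseline adjustment.

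Nor is this a false-positive problem. Unconditional type I error is near nominal, and the raised rejection rate appears only in the selected trials with a large baseline gap. The adjusted test itself ran slightly high, so a little of its apparent advantage may be liberality.

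Finally, Aim 2b is exploratory, no power is claimed for it, and the statement "Calculated effect sizes will be used for sample size estimation needed for a two-sided alpha of 0.05 and power of 0.80" sits under the HbA1c aim. That limits the importance. It does not remove the case for stating the contrast before the data are seen.

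**Conclusion.** The point holds as a modest improvement. The GEE sentence omits baseline adjustment and names no post-randomisation contrast, and nothing elsewhere in the document supplies either.

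The size depends on the reading. With three response visits and a group main effect, the effect is diluted to two thirds. The cost is then roughly 20 to 45 points of power against a baseline-adjusted analysis, for gains of 20 to 30 points and moderate correlation. With follow-up visits only, there is no dilution and the cost is about 5 to 19 points, less at the extremes of power. Either way, chance baseline imbalance goes uncorrected. All power figures rest on assumed rates, effects, correlations and complete data; the documents supply none of these. For a small gain such as 30% to 40%, every version has little power.

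**What to change.** Replace the GEE sentence in section 7.1 with wording to this effect: for each activity threshold, a GEE logistic model will be fitted to the 3- and 6-month responses with group, visit, group-by-visit and baseline achievement of the same threshold; the intervention effect is the group contrast averaged over 3 and 6 months, and the visit-specific contrasts will also be reported.

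An acceptable alternative keeps all three visits as responses, constrains the arms to a common baseline proportion and tests the group-by-post-baseline term. Its power was within 2 points of the first version in simulation.

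The cost is one sentence, with no new data, visits or participants. There are two downsides. Under the first version the odds ratio is conditional on baseline status. With 30 per arm the robust-SE test may also be slightly liberal (about 0.05 to 0.08 in simulation), so the plan should name a small-sample variance correction.

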Because the proposed study is minimal risk, we will not establish an independent Data Safety and Monitoring Board. The study team including several experts (Drs. [name], Hu) who have extensive experience in conducting clinical trials will perform data safety and monitoring. We will meet regularly to review inclusion and exclusion criteria, and develop a detailed safety protocol, plans for monitoring subjects for adverse events, and a protocol for protection of privacy and confidentiality of participants. The study PI ([name]) will hold weekly project meeting with the study staff and provide project updates to [name] (primary mentor) via weekly mentoring one-on-one meetings. The study PI will provide updates on the study progress, recruitment,

retention, data quality, safety, confidentiality, and the occurrence of adverse events to the whole mentoring team during bi-monthly check-in meetings.

The whole team will provide oversight for the following study procedures:

- Monitoring the safety of the subjects (e.g., review the research protocol and plans for data and safety monitoring)
- Evaluate the progress of the clinical trial, including periodic assessments of data quality and timeliness, subject recruitment, accrual and retention, subjects risk versus benefit, performance of the recruitment site, and other factors that can affect study outcome
- Maintaining the confidentiality and integrity of the data
- Reports of critical or adverse events from research staff. The PI will receive these reports on an event-by-event basis and will inform the whole study team of all such reports
- Make recommendations to the IRB and investigators concerning continuation or conclusion of the trial.

9. STUDY RECORDS RETENTION AND DATA SHARING

We are firmly committed to sharing data with the scientific community so that the data generated from this study can be fully utilized for research. Provided below is the proposed data-sharing plan:

1. We will publish the detailed methodology used for this study. Aggregated statistics will be provided to the broad scientific community via a journal's website or to an individual investigator/team upon request.
2. We will release the data generated from all study participants to qualified researchers who wish to collaborate with the investigators from our study. Investigators who wish to collaborate should submit a proposal that will be reviewed using criteria similar to those used by the NIH for scientific merit and human subject protection. All data should be used for research only. No data will be provided that could potentially disclose the identities of study participants.

NIH may release new policies regarding data sharing during the study period. We will be willing to discuss such policies with NIMHD program officers and modify the data-sharing plan detailed above.

